15.3 Criteria for the premature withdrawal of the subject

Criteria for premature withdrawal

The following criteria will cause a mandatory withdrawal from the study:

The reasons for a patient leaving the study prematurely may be the following:

- Subject's decision. The patient who wishes to leave the study for any reason can do so at any time, but must inform the researcher. In all cases, the investigator should attempt to establish contact with the patient as soon as possible for a final evaluation in order to:
 - Document the patient's decision in clinical notes,
 - Obtain the reason (s) for the exit and write them down in the FRC exit format,
 - Evaluate the patient's clinical status,
 - If necessary, take the appropriate therapeutic measures: management of an adverse event.

In case of failure of all these attempts to contact the patient, the investigator may declare "loss of follow-up" of the patient. The investigator will document all the attempts in the corresponding medical file.

- Decision of the investigator. Especially if an adverse event occurs and the researcher considers that this may threaten the patient's health, or if an important disease occurs that requires the prescription of a medication incompatible with the objective of the study.
- Need for another treatment according to the criteria of the Medical Investigator who will have to document it well in his notes.
- Pregnancy (see procedure in Appendix 2)
- Any deviation to the protocol that affects the patient's safety.
- In all cases, the available data will be saved for the safety analysis (population evaluable by intention to treat).

Process

Whatever the reason for the premature discontinuation of the study treatment, the investigator should immediately inform Laboratorios Sophia S.A. of C.V. and the patient must return the rest of the study treatments to the center.

In case of premature withdrawal of treatment, the investigator should record the reason (s), the exact date of the premature discontinuation of the treatment in the source document and in FRC. If more than one reason is given, the investigator must indicate the main reason.

In case of premature withdrawal from the study due to an adverse event (an event that is serious or not serious), the investigator should make every effort to gather information related to the outcome of the event. If necessary, the information will be collected later. This information will be recorded in the FRC part related to non-serious adverse events and serious adverse events in a format that will be given separately in case the investigator can not collect the information in a visit, then it will be obtained from the doctor who ensures the patient follow-up

If the study is discontinued / the treatment is discontinued as a result of an event that requires immediate notification, the procedure described in the suspension or discontinuation section of the study will be implemented.

16 TREATMENT OF STUDY SUBJECTS

16.1 Managed treatments

Lagricel Ofteno® Apply one drop 4 times a day for 7 days + any of the following according to the randomization in both eyes.

Apply one drop of PRO157, 2 TIMES a day, from day 1 to day 7
Apply one drop of PRO157, 3 TIMES a day, from day 1 to day 7
Apply one drop of PRO157, 4 TIMES a day, from day 1 to day 7
Apply a drop of Moxifloxacin, 3 TIMES a day, from day 1 to day 7
Apply a drop of Gatifloxacin, 3 TIMES a day, from day 1 to day 7

16.2 Delivery of the treatment

The study drugs will be delivered by a coordinator (not blinded) or person previously designated by the principal investigator, who will indicate how to apply the study medication according to the randomization and will make special emphasis to each subject of not mentioning the principal investigator or person previously designated to perform the treatment evaluations as the drop or characteristic of the delivered bottles is applied.

This is to keep the blind person in the subject's evaluator and avoid bias.

16.3 Previous and concomitant treatments

Prohibited treatments

Table 4 shows the list of prohibited treatments during the study.

If a prohibited treatment is absolutely necessary during the study, the subject should be removed from the study.

Table 4. Main prohibited treatments (during the study)

Medicamento		Vía de administración
Grupo	Prototipo	
Betalactámicos	Penicilinas, Cefalosporinas, Monobactams, Carbapenems.	Tópica
Aminoglucósidos	Gentamicina	Tópica
Azúcares complejos	Clindamicina	Sistémicas
Polipeptídicos	Polimixina	Tópica
Rifamicinas	Rifampicina	Sistémica
Tetraciclinas	Clortetraciclina	Tópica
Amfenicoles	Cloramfenicol	Tópica
Macrólidos	Eritromicina	Sistémico
Miscláneos	Espectinomicina, Virginiamicina, Vancomicina, Teicoplanina, Capreomicina, Cicloserina, Fosfomicina, Novobiocina, Linezolida	Tópica, Sistémico
Quimioterapicos antibacterianos	Sulfonamidas Sulfonamidas + Trimetoprim Nitrofuranos Derivados de Naftiridinay Quinolonas	Tópica, Sistémico
Antiinflamatorios no esteroideos	Ketorolaco. Diclofenaco, nepafenaco, meloxicam,	Tópica
Esteroides	Prednisolona, dexametasona, triamcinolona, fluorometolona, loteprednol.	Tópica, Sistémico
Lagrimas artificiales con conservador		Tópica
Antihistamínicos	Epinastina	Tópica
Descongestionantes	Nafazolina , Oximetazolina, etc	Tópica
Estabilizadores de mastocitos	Cromoglicato de Sodio, etc	Tópica
Quinolonas 3era o 4ta generación	Moxifloxaciono. Gatifloxacino	Tópica
Quinolonas 2da, 3era o 4ta	Ciprofloxacino, Levofloxacino, Ofloxacino.	Sistémicas.

16.4 Authorized treatments during ophthalmologic exploration and / or course of study

Tretacaine hydrochloride (during ophthalmologic exploration)
Tropicamide / Phenylephrine Hydrochloride (during ophthalmologic exploration)
Lagricel Ofteno® (during the whole study time)

16.5 Compliance with treatment

- With the accounting of the study medication returned.

- Patients will have a "diary of the subject" where they will have to write down the time of application of the drop and any incident or setback at the time of the application of the drop, for example, forgetfulness in the application of the drop, application of extra drops, etc.

- The adherence to treatment must be greater than 80%

After the discontinuation of the study treatment, the subject will return with the previously used treatment.

17. Methods and times of measurements.Scales to fill out by the researcher:

A meeting of researchers will be organized for all those involved in carrying out the study before starting it, and their participation will be mandatory. The objective of these sessions is to train them on the assessment of the efficacy and safety criteria and to ensure reliability among the qualifiers. In addition, detailed qualification rules will be provided to the qualifiers

The scales should always be evaluated by the same evaluating physician, either the principal investigator or an ophthalmologist previously designated in the Delegation of Responsibility format throughout the study, at the beginning of each visit. A guide will be made available for the interview to be carried out in each of the visits.

Self-qualification questionnaires to be completed by the patient:

Initials of the subject	
-------------------------	--

Mark with an X in any of the following options with which you have identified more in the course of the clinical study.

DEGREE OF SATISFACTION OF THE SUBJECT	ANSWER
Very bad: Intense and unbearable nuisances.	
Mal: Moderate intensity, intermittent, not tolerable.	
Regular: Discomfort of moderate intensity, intermittent and tolerable.	
Good: Mild and occasional nuisances.	
Very good: No discomfort (absent).	

The researcher will apply to the subject a questionnaire that he / she will have to answer at the end of the study where the satisfaction is evaluated upon finishing his / her participation in the study.

Visual acuity

It is a measure of the ability of the visual system to detect and recognize spatial details, it is performed in a high contrast test and with a good level of illumination. To measure visual acuity (VA) a patient will be presented with different high contrast tests and different sizes at a fixed distance, and the value will be noted as far as the patient sees it. The smallest size that the patient recognizes will be taken as a threshold value and expressed in minutes of arc. Visual ability is the best corrected visual acuity.

Bailey and Lovie designed and proposed a primer that would standardize the answers for each letter size in each of the lines. This was achieved by using a logarithmic progression of the size of the optotypes, obtaining equality in the discernment. They proposed that each line of optotypes contain five letters and the space between them is exactly the size of the letters of the same line and the space between the lines is equal to the size of the optotype of the lower line. In such a way that with this booklet, Bailey and Lovie innovated the method of assessing visual acuity through the logarithm of the minimum resolution angle (logMAR). This type of scale establishes: 1) the visual acuity 20/20 is equal to 0.00 in logMAR and 2) the 20/200 represents in log MAR the unit (1,0). Therefore, each successive line change represents a change of 0.10 logarithmic units. In a line of five letters each letter has a value of 0.02 logarithmic units; in this way, the value of the acuity reached within a line can be objectively annotated. This makes the test have a high degree of reliability. In the area of research, it is called a "Golden Proof".

Standardization of the visual examination:

- At a distance of 3 m in a room with dim lighting, the research subject will be evaluated as follows:
 - This exam will be held at the research center
 - The patient will be asked to always sit in the same place and with the LogMar scale the visual acuity (AV) will be assessed if he / she does not have this type of booklet he / she must carry out the conversion.
 - The research subject will keep both eyes open.
 - The research subject should gently cover one eye with an occluder while reading aloud the smallest line of letters that can be seen. This test is done on each eye, one at a time, starting with the right eye (RE).
 - The doctor must point out, the line that is requested to read the research subject.
 - Finally, through the pinhole, the same procedure will be carried out.

Normal values: visual acuity or visual capacity will be expressed in decimals, where 0.0 will be the maximum normal score. In the case of people who do not know how to read, the test will be done with special cards of figures or numbers and the VA will be defined with the same LogMar scale, for patients of very early ages such as RN, infants or uncooperative preschoolers. AV as it perceives and follows light or does not perceive or follow light.

In offices where LogMar is not available, you can measure the VA with the card you normally use and convert it to the LogMar scale for which the following table of equivalences helps.

Equivalence between the different AV scales

MAR (min arc)	Log MAR	Snellen (d=6m)	Snellen (d=20 ft)	Escala decimal	Keeler A
100	2.0	6/600	20/200	0.01	
79	1.9	6/480	20/1600	0.0125	20*
63	1.8	6/380	20/1250	0.016	19*
50	1.7	6/300	20/1000	0.02	18*
40	1.6	6/240	20/800	0.025	17*
32	1.5	6/190	20/630	0.032	16*
25	1.4	6/150	20/500	0.04	15*
20	1.3	6/120	20/400	0.05	14*
15.8	1.2	6/95	20/320	0.063	13*
12.5	1.1	6/75	20/250	0.08	12
10.0	1.0	6/60	20/200	0.1	11
8.0	0.9	6/48	20/160	0.125	10
6.3	0.8	6/38	20/125	0.16	9
5.0	0.7	6/30	20/100	0.2	8
4.0	0.6	6/24	20/80	0.25	7
3.2	0.5	6/19	20/63	0.32	6
2.5	0.4	6/15	20/50	0.4	5
2.0	0.3	6/12	20/40	0.5	4
1.58	0.2	6/9.5	20/32	0.63	3
1.25	0.1	6/7.5	20/25	0.8	2
1.0	0.0	6/6	20/20	1.0	1
0.8	-0.1	6/4.8	20/16	1.25	
0.63	-0.2	6/3.8	20/12.5	1.6	
0.5	-0.3	6/3	20/10	2.0	

Biomicroscopy Previous

It refers to the revision of the entire anterior segment: cornea, iris, pupil, anterior chamber, crystalline and / or (IOL).

It will be qualified as follows:

Normal.

Abnormal.

Abnormality that does not affect the result of the study.

If any of the structures has any special description that you write down in comments of that same section in the FRC.

Conjunctival hyperemia

Which is defined as the simplest reaction of the conjunctiva to a stimulus, we see a red appearance secondary to the vasodilation of the conjunctival vessels of variable intensity. It will be classified according to the analogous visual scale of hyperemia. VII

1.- Very Mild

2. Mild

3.- Moderate

4.- Severe

Foreign body sensation

Burning

Lachrymation

Eyelid scales

Eyelid edema

Membranes and / or pseudomembranes

Epitheliopathy

These symptoms will be described as present or absent,

Secretion will also have to be described

Fluorescein and green lysamin stain

Fluorescein staining will be performed, standardization of this scan is done as follows:

1. With the patient in front of the lamp prior instillation of topical anesthesia Ponti Ofteno that will be provided by Laboratorios Sophia, S.A. of C.V.
- 2.- The lower eyelid of the patient will be gently grabbed, first on the right side and then on the left side, asking the patient to turn upwards so that with this maneuver a greater area of the lower bulbar conjunctiva is exposed, then the filter paper will be placed moistened with a drop of anesthetic and the surface of the eye will be touched with it for a second in the aforementioned area, subsequently the patient will be asked to blink several times and proceed to examine it without specifying corneal region, the same procedure will be performed for the analysis of the conjunctiva with lysamine green:

Absent (without staining)

Medium (less than 10% of the surface with staining)

Moderate (from 10 to 50% with surface staining)

Severe (more than 50% of the surface)

Membranes and pseudomembranes

They are formed by exudates adhering to the inflamed conjunctival epithelium, the difference between one and another is that the latter are removable.

Your presence or absence will be reported.

Subsequent Segment Review

It refers to the revision of the entire posterior segment, particularly: vitreous, retina, macula and optic nerve. It will be qualified as follows:

Normal.

Abnormal.

Abnormality that does not affect the result of the study.

If any of the structures has any special description that you write down in comments of that same section in the FRC.

Sampling for central laboratory:

(This is a general procedure, it does not mean that it should be done as such, that procedure will be punctually described by the central laboratory where the crops will be sent).

- 1.- After cleaning hands and putting on latex gloves.
- 2.- Take the swab contained in the package of the means of transport with the index fingers and thumb of the right hand while with the index finger of the left hand the lower eyelid is gently pulled exposing the bottom of the bag and thus be able to take the sample of it
- 3.- By touching the palpebral conjunctiva the applicator is rotated to take as much sample as possible.
- 4.- Place the swab in the transport medium.

The central laboratory in charge of the processing of the samples will be asked for Gram stain and special attention to the growth in the culture of the following bacteria:

Staphylococcus aureus, Staphylococcus albus, Pseudomonas aeruginosa, Streptococcus pneumoniae, Haemophilus influenzae, Streptococcus pyogenes, Klebsiella pneumoniae Escherichia coli, Neisseria gonorrhoeae, Streptococcus viridans, Moraxella catarrhalis.

The technique for collecting the sample will be done using a swab. These techniques are not limiting, and it is up to the doctor to select one of them according to the case.

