• The safety of the use of PRO-157 will be evaluated in the visits indicated in the schedule, through the following parameters:

1. Visual capacity
2. Eye surface
3. Exploration of the previous segment
4. Exploration of the posterior segment
5. Burning
6. Foreign body sensation
7. Lachrymation
8. Conjunctival hyperemia
9. Itching
10. Photophobia
11. Chemosis
12. Tear discharge
13. Eyelid edema
14. Membranes / pseudomembranes
15. Scales
16. Corneal epithelial defects
17. Adverse events

It will be considered that the drug under evaluation is safe for use in humans if there are no changes in the parameters indicated in more than 5% of the subjects, in both eyes, if the

patient goes to all the visits of the study and complies with adherence to treatment $\geq 80\%$ during the time of evaluation of the study.

Variable	Operationalization	Measurement scale	Value
Visual ability	Independent Discrete quantitative	Points logMAR 0-1 0 = Snellen 20/20	Do not present change in 1 line in the Snellen letter or in 1 logarithmic point (log MAR)
Ocular surface	Dependent Qualitative ordinal	Absent Present	Abnormalities in any area of the ocular Surface
Exploration of the previous segment	Dependent Qualitative ordinal	Normal Abnormal	Abnormalities in any of the structures included: cornea, iris, pupil, irido-corneal and crystalline angle.
Exploration of the posterior segment	Dependent Qualitative ordinal	Normal Abnormal	Abnormalities in any of the structures included: vitreous, retina, macula and the optic nerve
burning	Dependent Qualitative ordinal	Absent Present	Must be recorded as absent in 95% of the subjects evaluated
strange body sensation	Dependent Qualitative ordinal	Absent Present	Must be recorded as absent in 95% of the subjects evaluated
tearing	Dependent Qualitative ordinal	Absent Present	Must be recorded as absent in 95% of the subjects evaluated

Secretion	Dependent Qualitative ordinal	Absent Present	Must be recorded as absent in 95% of the subjects evaluated
Conjunctival hyperemia	Dependent Qualitative ordinal	Absent Mild Moderate Severe	You must comply with the following: Absent ≥ 95.0% Mild ≤ 5.0% Moderate ≤ 2.5% Severe ≤ 1.0%
Photophobia	Dependent Qualitative ordinal	Absent Mild Moderate Severe	You must comply with the following: Absent ≥ 95.0% Mild ≤ 5.0% Moderate ≤ 2.5% Severe ≤ 1.0%
Chemosis	Dependent Qualitative ordinal	Absent Present	Must be recorded as absent in 95% of the subjects evaluated

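### The safety table records visual capacity on logMAR 0 to 1, but the plan's own conversion table runs from 2.0 to -0.3; a literal floor at 0 hides line losses in eyes better than 20/20, and card distance and the change unit are also unreconciled.

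*Combined protocol and SAP*

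**What the plan says.** Section 7.1, in the safety table's row for visual ability, gives the measurement scale as "Points logMAR 0-1 0 = Snellen 20/20". The value that the variable must meet is "Do not present change in 1 line in the Snellen letter or in 1 logarithmic point (log MAR").

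Section 17 (Methods and times of measurements, Visual acuity) anchors logMAR at 0.00 for 20/20 and 1.0 for 20/200, and states that "each successive line change represents a change of 0.10 logarithmic units". Under normal values it describes acuity as expressed in decimals, "where 0.0 will be the maximum normal score". The equivalence table that follows has 24 rows from logMAR 2.0 to -0.3. Its last row reads "0.5 -0.3 6/3 20/10 2.0" (MAR, logMAR, two Snellen notations, decimal).

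On technique, the standardised examination is done "At a distance of 3 m in a room with dim lighting", and a site without a logMAR booklet must convert. For such sites Section 17 adds that "you can measure the VA with the card you normally use and convert it to the LogMar scale". The table's two Snellen columns are headed 6 m and 20 ft; the MAR and decimal columns carry no distance. No sentence says at what distance the usual card is read, or how to correct if that is not the card's own distance.

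**The concern.** The recorded range and the conversion table disagree. Of the table's 24 rows, 3 lie below 0 and 10 lie above 1.0, so 13 have no place on the scale in Section 7.1. Two sites could score the same eye differently, each with support in the text.

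The direction matters. A floor at 0 can only make losses look smaller. Section 17 defines visual ability as best-corrected acuity and adds a pinhole reading, and both push values towards the end that would be cut. Section 7.1 calls the drug safe if the listed parameters do not change in more than 5% of subjects. If that is applied per arm, 60 eyes come from 30 to 60 subjects, and the limit is crossed by 2 of 30 or 4 of 60 (6.7% each). A few unrecorded losses could matter at that scale.

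The 3 m distance next to columns headed 6 m and 20 ft raises a second question: whether sites using the fallback record acuity that is too good.

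**Working it through.** **1. Check of the plan's table.** logMAR = log10(MAR) = log10(6 m denominator / 6) = log10(20 ft denominator / 20) = -log10(decimal). All 24 rows agree to within 0.01, with one exception. The 20 ft entry beside logMAR 2.0 is printed as 20/200, but log10(200/20) = 1.0, and 2.0 corresponds to 20/2000. As printed, 20/200 stands against both 2.0 and 1.0. This entry should be checked in the source file.

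**2. Floor at 0, card at its own distance.** Recorded change = clip(final, 0, 1) - clip(baseline, 0, 1), in lines of 0.10 (Section 17).

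| True baseline | Recorded loss for true losses of 1, 2, 3, 4 lines |
|---|---|
| -0.3 | 0, 0, 0, 1 |
| -0.2 | 0, 0, 1, 2 |
| -0.1 | 0, 1, 2, 3 |
| 0.0 or worse (checked to 0.4) | 1, 2, 3, 4 |

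For example, an eye that goes from -0.2 (20/12.5) to 0.0 (20/20) has lost two lines and is recorded as 0.0 both times. An eye that goes from 0.0 to 0.1 is recorded correctly as a one-line loss.

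**3. 6 m card read at 3 m, no floor.** Error = log10(3/6) = -0.301, about three lines too good. The change is (final - 0.30) - (baseline - 0.30) = final - baseline, so losses of 1 to 4 lines are recorded as 1 to 4. The offset cancels as long as card and distance do not change between visits.

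**4. Both together.**

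| True baseline | Recorded loss for true losses of 1, 2, 3, 4 lines |
|---|---|
| -0.1 or better (checked to -0.3) | 0, 0, 0, 0 |
| 0.0 | 0, 0, 0, 1 |
| 0.1 | 0, 0, 1, 2 |
| 0.2 | 0, 1, 2, 3 |
| 0.3 or worse (checked to 0.4) | 1, 2, 3, 4 |

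Only in this combination does a 20/20 eye hide losses, of up to three lines.

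**5. Threshold unit.** One line is 0.10, so one logMAR point is 1 / 0.10 = 10 lines. That is the whole 0 to 1 scale, from 20/20 to 20/200. The Section 7.1 row offers one line and one point as alternatives.

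**6. Illustration only.** The documents give no baseline acuity. Assume normal baselines with SD 0.12, rounded to the 0.1 grid, at the correct distance. The share of one-line losses hidden by the floor is Phi((-0.05 - mean)/0.12). For assumed means of -0.10, -0.05, 0.0 and 0.10 this is 66%, 50%, 34% and 11%. For two-line losses, Phi((-0.15 - mean)/0.12) gives 34%, 20%, 11% and 2%. The spread shows how far any percentage depends on the assumed mean.

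**The case against.** The strongest reply is that no floor is ordered. The Section 17 sentence on 0.0 stands under normal values and can be read as a reference value. The table beneath it gives sites rows below 0 and above 1.0 to convert into, and nothing tells them to truncate. This stands as far as that sentence goes. It does not dispose of Section 7.1, where 0 to 1 is entered as the measurement scale of the safety variable. The documents contradict each other, and one of the two readings loses information.

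Three stronger inferences are tempting, and the documents do not support them.

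- *Losses in 20/20 eyes are scored as no change.* With the floor alone they are not (step 2).
- *The distance mismatch itself biases the safety result.* A constant offset cancels within an eye (step 3). Section 17 asks for the same seat and the same evaluator at each visit, although it does not fix the card. Nor do the documents establish that a 6 m card is read at 3 m. The 3 m instruction makes it possible, but a chart made for 3 m, or a card used at its own distance, converts without error.
- *A known share of losses is missed.* Neither the share of eyes better than 20/20 nor the share of sites using the fallback is given. Infants and uncooperative preschoolers are scored only on following light, outside this scale.

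It is also fair to say that the safety rule lists 17 parameters, and that nothing suggests the error would differ between arms.

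**Conclusion.** The point holds as a contradiction in how a named safety variable is recorded. If Section 7.1 is followed literally, baselines of -0.1, -0.2 and -0.3 hide losses of up to 1, 2 and 3 lines, and eyes worse than 1.0 have no recordable value. The distance gap is a conditional second problem. If a 6 m card is read at 3 m, acuity is recorded 0.30 logMAR too good; within-eye change survives unless a floor at 0 also applies, in which case a 20/20 eye can hide losses of 1 to 3 lines. The threshold row separately treats one line and ten lines as alternatives.

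The size in eyes or subjects cannot be computed from the documents. A reader might infer a demonstrated bias in the safety conclusion, but the text supports only a rule that would give wrong results under its literal reading.

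**What to change.** - In Sections 7.1 and 17, state that the recorded range is the full equivalence table, -0.3 to 2.0 logMAR, with no floor at 0.0 and no cap at 1.0. On an unbounded scale, losses of 1 to 4 lines are recorded correctly at every baseline checked from -0.3 to 0.4, even with a constant distance offset.
- In Section 17, have each site test at the distance its card is calibrated for, or correct before converting (add log10(6/3) = 0.30 logMAR for a 6 m card read at 3 m). This is needed for correct absolute values.
- Keep the same card and distance for a patient at all visits, and record both on the case report form. A switch between a 6 m card at 3 m and correct testing would by itself create an apparent change of about three lines.
- In the same Section 7.1 row, reconcile the one-line and one-logMAR-point criteria with the 0.10 per line in Section 17.
- Check the 20 ft entry beside logMAR 2.0.

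The cost is wording in two sections and one form entry, with no added visits or staff.
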